## **8. Risks**

- a. Medical risks, listing all procedures, their major and minor risks and expected frequency.

Hydromorphone: Our research team has extensive experience administering hydromorphone under controlled laboratory conditions. Administration of any drug involves some risk because it is not always possible to predict individual response to drugs. The most likely risk in this study is that subjects will experience side-effects of the drugs that may be unpleasant. Common side effects of hydromorphone are light-headedness, dizziness, sedation, nausea, vomiting, sweating, flushing, dysphoria, euphoria, dry mouth, and pruritus. Less frequently observed side effects are weakness, headache, agitation, tremor, uncoordinated muscle movements, alterations of mood (nervousness, apprehension, depression, floating feelings, dreams), muscle rigidity, paresthesia, muscle tremor, blurred vision, nystagmus, diplopia and miosis, transient hallucinations and disorientation, visual disturbances, insomnia, increased intracranial pressure, flushing of the face, chills, tachycardia, bradycardia, palpitation, faintness, syncope, hypotension, hypertension, bronchospasm and laryngospasm, constipation, biliary tract spasm, ileus, anorexia, diarrhea, cramps, taste alteration, urinary retention or hesitancy, antidiuretic effects, urticaria, other skin rashes and diaphoresis. Side effects of hydromorphone are generally temporary, dissipate within several hours, and are dose-dependent. Thus, participants may only experience side-effects occasionally during the research study. Serious potential adverse effects of hydromorphone administration that are possible but extremely unlikely to be encountered in this study are respiratory depression and loss of consciousness. The most serious potential adverse event following hydromorphone administration is opioid agonist overdose, which is characterized by respiratory depression, somnolence progressing to stupor or coma, skeletal muscle flaccidity, cold and clammy skin, constricted pupils, and sometimes bradycardia and hypotension. In serious overdosage, particularly following intravenous injection, apnea, circulatory collapse, cardiac arrest and death may occur. We believe the risk of respiratory depression leading to overdose in this study to be low for the following reasons: we have extensive experience in the administration of hydromorphone, we have chosen doses that have been demonstrated directly by us in several previous laboratory studies (99-102) to be safe and tolerable in an identical participant population, we will exclude any individual who has a medical condition that may increase the risk for respiratory depression and/or other adverse events, all medication doses will be administered by a trained research nurse, and participants will be monitored 24-hours by trained staff who will have access to the opioid antagonist naloxone to reverse the opioid agonist effects.

Chance That Participants May Begin Abusing Opioids Following Exposure to Study Hydromorphone: There is a small but potential risk that exposing non-drug abusing individuals to doses of hydromorphone designed to elicit reinforcing effects may precipitate subsequent drug-use behavior. Enrolling non-drug users into controlled laboratory studies is a conventional strategy that has been used extensively to evaluate the abuse liability potential of numerous drugs of abuse both within our laboratory and by other laboratories. We feel confident this strategy imposes minimal risk on the participants, and have provided justification for this assertion in the Protection Against Risks section.

Risks Associated with Genetic Analysis: We have established several precautions to prevent breach of confidentiality regarding genotype status that are discussed in the Protection Against Risks section. There is a low risk for breach of confidentiality regarding genotype status and that a participant's genetic information can be linked to his or her questionnaire assessments.

Discomfort from Pain Testing: Participants will likely find the pain testing procedures uncomfortable for a brief period of time. This effect is expected to be transient and to produce only mild levels of discomfort.

Breach of Confidentiality: Although staff members are highly trained to maintain participant confidentiality, there is always a risk that some of the confidential information collected could be revealed to people who are not involved in

the research study. This could be embarrassing to the participant if the participant preferred to keep his or her study participation secret, or if sensitive information became known to an individual outside the study. We have an extensive history of conducting research among substance abusers and have instituted several practices to prevent a breach from confidentiality from occurring (see below); thus, we believe this risk to be minimal.

b. Steps taken to minimize the risks.

Prior to study enrollment, a medical staff member carefully screens participants to exclude those with an increased risk of adverse events. Trained nursing staff member conducts all medication administrations, and a code to break the drug blinks is always available if needed. Specific protection against risks are outlined below.

Protection Against Hydromorphone Risks: We also have extensive experience in the administration of hydromorphone and other opioid agonists in controlled laboratory settings and therefore anticipate few problems. Any individual who may be prone to the risks associated with hydromorphone will be excluded from participating. The FDA has identified the following conditions as increasing the risk for respiratory depression or other serious side effects following hydromorphone administration: patients with status asthmaticus; chronic obstructive pulmonary disease; reduced respiratory function; high blood pressure; impairment of hepatic, pulmonary or renal functions; myxedema or hyperthyroidism; adrenocortical insufficiency; gall bladder disease; acute alcoholism; history of convulsive disorders; history of head injury; currently taking sedatives, hypnotics or phenothiazines; and sulfite allergy. Mean exposure to hydromorphone is also increased 4-fold among patients with hepatic impairment and 3-fold among patients with renal impairment. Therefore, to further reduce the risk serious side effects, we will exclude any potential participant who exhibits one or more of these conditions. Second, although research staff and participants will be blinded to the exact medication provided, both groups will be informed of the potential side effects and risks associated with the study drug administration. Third, participants will be free to discontinue study participation at any time without consequence. Great care has been taken in selecting the appropriate drug doses to ensure hydromorphone is well-tolerated and safe for our participants. Fourth, standard concomitant medications (e.g., anti-nausea medications) will also be available as needed to treat any unpleasant side effects that may occur as a result of hydromorphone administration and participants will also be able to discontinue study participation at any time. Finally, the most serious risk associated with hydromorphone administration is respiratory depression. We believe this risk is minimal in this study for several reasons. First, we have selected a range of equipotent doses that we have previously demonstrated to be safe and well-tolerated in the same participant population (non opioid dependent individuals) (99-102) and based upon a previous study that piloted and ultimately administered identical doses to an identical research sample (136). Second, we have developed several standard criteria that are followed by nursing staff and research personnel to monitor participants who have been provided with a study medication. All nursing and research staff are informed of these standards, and a list of these standards is posted in each testing room. The standards are as follows: If respiratory rate drops below 8 breaths/minute and is accompanied by sedation, participants are prompted verbally to breath. In our experience, verbal and physical stimulation is often sufficient to prompt breathing and restore a normal respiratory rate. If respiratory rate drops further and/or if oxygen saturation rates fall below 90% saturation, successive dosing is terminated. Patients are monitored carefully with a “watch and wait” approach; during this period they are accompanied continuously by a medical and/or nursing staff member, evaluated by a staff physician, and are given supplemental oxygen at 2L/min via a nasal cannula (available on site in the exam testing room). If clinical evaluation determines that a participant’s sedation level is increasing, the opioid antagonist naloxone can be promptly administered via intramuscular route to produce an immediate reversal of opioid effects. There have been very few incidents throughout our >15 year experience administering opioid agonists to human participants in controlled laboratory conditions that have necessitated actual intervention (oxygen and/or naloxone), however our equipment and medical/nursing staff is always prepared for this possibility. We feel these procedures will sufficiently protect participants from possible adverse and serious adverse events. Finally, we will submit an annual review of study-related adverse and serious adverse events to the Johns Hopkins IRB and an independent group of consultants who will serve as our data safety monitoring board for evaluation.

Protection Against Chance That Participants May Begin Abusing Opioids Following Exposure to Study Hydromorphone: Another concern is the possibility that exposure of participants with no histories of drug abuse to drugs in our research setting might in some way increase the likelihood of these individuals to begin abusing illicit drugs when they return to the community. The Johns Hopkins IRB closely monitors this issue, and has repeatedly concluded that administering drugs that have reinforcing effects to individuals who do not abuse drugs is not associated with an increased propensity to begin abusing drugs. Administering drugs that may have reinforcing

effects to non-dependent users has substantial precedent in laboratory examinations of drug effects, and we have a rich and extensive history of utilizing this practice. Several research studies that have directly examined the association between study-related drug administration and subsequent drug use behavior have failed to demonstrate that controlled, laboratory drug exposure increases the risk for developing future dependence. For example, authors of a recent study that administered methamphetamine to a sample of non treatment-seeking drug abusers reported no difference between-group differences in drug use behaviors, assessed via the Addiction Severity Index, at a 6-month follow-up assessment (166). Second, a systematic follow-up study reported that alcohol-dependent volunteers randomly assigned to laboratory studies either involving or not involving experimental alcohol consumption have not differed in their follow-up outcomes (167). Third, a recent study concluded that investigational administration of intravenous cocaine to intravenous inexperienced cocaine users did not increase the risk of recreational intravenous use (168). Fourth, a study conducted by our research team administered cocaine and/or opioids to participants with histories of drug abuse and observed no significant changes in number of days of reported drug use, dollar amounts reported spent for various drug classes, or any increases in Addiction Severity Index domain scores at a one month follow-up (169). Finally, the College on the Problems of Drug Dependence, a prestigious international association of drug dependence researchers, supports the practice of enrolling non treatment-seeking individuals into drug abuse liability evaluation studies. Specifically, the College on Problems of Drug Dependence reported that exposure of drug abusers to abused drugs in a controlled research setting does not enhance the desire of an individual to use drugs, worsen addiction, or make addiction more difficult to treat (170). Overall, given the substantial data available in the literature and our own laboratory experience, we feel confident that administration of small quantities of opioids to individuals with recreational histories of drug abuse will not be associated with future drug use behavior. Ultimately, we feel the benefits of using this well-validated and heavily researched design to evaluate the association between OPRM1 status and abuse liability of hydromorphone outweighs the minimal potential risk that exposure to hydromorphone in a controlled research setting could precipitate subsequent drug use behavior. Second, the risk that drug administration may precipitate drug use behavior increases when the route of administration leads to a quicker onset of effects, as is the case with intravenous, intramuscular or intranasal administration. We have therefore chosen to administer hydromorphone in an oral formulation, which has the slowest onset of effects, in part to help mitigate this risk. Finally, both participants and research staff will be informed the study drug may consist of one or more numerous different drug classes (e.g., opioids, benzodiazepines, stimulants, over-the-counter medications); this is a widely used practice that helps reduce drug expectancy effects (97-98). This practice will also help protect against subsequent abuse because participants will not know exactly what compound produced the reinforcing effects they may have experienced.

Protection Against Risks Associated with Genetic Analysis: We believe the risks associated with breach of confidentiality regarding genetic status to be minimal because the proposed study does not fall into any of the categories identified by the NIDA Genetics Workgroup as being high risk for participants involved with genetic studies: (1) pedigree studies that aim to discover the pattern of inheritance of a disease and to catalog the range of symptoms involved; (2) positional cloning studies that aim to localize and identify specific genes; (3) DNA diagnostic studies that aim to develop techniques for determining the presence of specific DNA mutations; and (4) gene therapy research that aims to develop treatments for genetic disease at the DNA level. In addition, we can identify no *a priori* defined ethical imperative that would necessitate disclosure of the genetic testing results. For instance, given the relatively specific eligibility criteria, it is unlikely we will be enrolling members of families. Second, there is not an established association between OPRM1 status and the development of any disease- including substance abuse. If new information becomes available that unequivocally indicates a direct link between a genetic polymorphism in the OPRM1 and the development of disease, we will consult with the Johns Hopkins IRB regarding any ethical imperative that participants be informed of their OPRM1 status.

Discomfort from Pain Testing: It is likely that participants will experience some acute and transient discomfort from the pain testing session, however we will work to mitigate that risk as much as possible. First, participants will be informed of the pain testing procedure during the informed consent and will be able to make an informed decision regarding their study participation. Second, we chose pain tests (pressure pain and conditioned pain modulation) that will produce short-lived effects, and are unlikely to produce any residual pain. Third, we will stop pain administration as soon as participants report the first incidence of “pain” (operationalized as 50% on a scale of 0% (no pain) to 100% (extreme pain)). Time to first pain will serve as our dependent variable in the analyses. Fourth, we will enforce an upper limit on both pain measures to prevent any tissue damage from occurring (e.g., hand cannot be in cold pressor task for >150 seconds). Fifth, participants will be informed that they can revoke their consent to participate in the pain testing at any time without penalty. Finally, the participants will be monitored 24 hours by

study staff and will have access to medical care and concomitant medications to treat residual pain if necessary. We will also document and submit to our DSMB all adverse events reported from the pain testing session and will follow any recommendations they may have regarding the cessation of pain testing.

Protection Against Risks Associated with Confidentiality: To protect confidentiality, all research participants will be assigned unique participant identification codes that will be used on all study-related forms and online websites. Documents that include the participants' full names (e.g., signed informed consent forms) will be stored in an independent binder, consistent with FDA Good Clinical Practice Guidelines, and will be kept in a locked room. Confidential information will never be shared with anyone outside of the research program without the explicit written permission of the research participant. Only selected designated staff members will be approved to share confidential information after explicit written permission is obtained from the participant and the participant will be able to revoke written permission at any time. In accordance with IRB requirements, all research staff will be formally trained in these procedures. No identifying participant information will be used in written reports, manuscripts and/or conference presentations.

c. Plan for reporting unanticipated problems or study deviations.:

All adverse events will be reported to the IRB and other relevant agencies (e.g., FDA, NIDA) as required and as described in the DSMP. The Principal Investigator and Co-investigators are responsible for reporting such events.

d. Legal risks such as the risks that would be associated with breach of confidentiality.:

Although there is always a small risk that confidentiality will be breached, we believe this risk to be very minimal with the current study.

e. Financial risks to the participants. None.

**9. Benefits**

Description of the probable benefits for the participant and for society: The long-term goal of this research is to investigate individual differences in response to opioids, and identify genetic differences that contribute to variations in the susceptibility of opioid dependence. The objective of this application is to determine whether the OPRM1 gene predict one of several opioid-mediated effects using a rigorous, controlled laboratory study among healthy individuals with no history of drug dependence and whether this effect differs as a function of gender. This study will constitute the most controlled, rigorous, comprehensive examination of the OPRM1 gene association with opioid-mediated effects to date. We expect that genotype will be associated with several opioid-mediated effects. These results are expected to have a positive impact by advancing our understanding of the association between the OPRM1 gene and opioid-mediated effects, including susceptibility for opioid dependence. These data will provide positive contributions to the field of pharmacogenomic medication prescribing, the development of opioid dependence prevention strategies and interventions to treat comorbid pain and opioid dependence, and will have implications for other MOR-mediated effects, including alcohol dependence.

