#### 4. Study Procedures

- a. Study design, including the sequence and timing of study procedures (distinguish research procedures from those that are part of routine care).

**Study Overview:** This study will be a between-group (total completer N=100) evaluation of genotype and sex, and a within-subject evaluation of opioid dose-response. The study will be conducted over 5 days (4 nights) at the Behavioral Pharmacology Research Unit (BPRU) and a residential clinical research unit (CRU) (Figure 1). Day 1 will be an Admission day. Days 2-5 will consist of blinded study drug administration in the morning, 1 pain testing session, and self-report/physiological measures of drug effects for 6 hours post dosing. Participants will receive double-blind doses of oral hydromorphone (2mg, 4mg, 8mg) (99-102) or weight and color-matched placebo in a randomized, counter-balanced research design.

**Screening Visit:** Participants will complete a brief phone screen to determine initial eligibility and will be invited to complete an in-clinic screen. Participants will sign an informed consent form with a study staff member to begin the Screening visit. To reduce expectancy effects, the consent will inform participants the study drug may consist of one or more of numerous different drug classes (e.g., opioids, stimulants, over-the-counter medications), a common practice in laboratory based studies of drug effects (103, 104). Following consent, a staff member will administer a battery of measures to establish study eligibility (see Study Measures below). A urine sample will be collected and tested for evidence of illicit drugs and to establish medical eligibility. A blood sample of no more than 2 tablespoons will also be collected from eligible participants for medical and genotype analysis. Participants will also be asked to provide a second blood sample (2 additional tablespoons) that will be collected at either Screening or Admission and stored for future genetic analysis. This will be voluntary. Participants who meet eligibility criteria (including results of laboratory blood tests) will be scheduled for an Admission day.

**Study Day 1, Admission Visit:** Participants will complete a brief history and physical to determine final study eligibility and will be admitted to the CRU for 5 days (Admission day + 4 session days). During the Admission day, participants will be familiarized with the pain testing procedures and the measures used during session days 2-5.

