	10. Presence of any clinically significant medical (e.g., chronic renal insufficiency, history of myocardial infarction, seizure disorder) and/or psychiatric illness (e.g., schizophrenia, bipolar disorder) that may interfere with study participation.
	11. BMI >30 (obese category)

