Hydromorphone hydrochloride is a pure mu opioid agonist that can be administered in oral, rectal, intramuscular (IM), or intravenous (IV) formulations for the indication of acute and/or chronic pain. We have chosen to administer hydromorphone orally in this study to reduce the potential for side effects and adverse events associated with the more direct parenteral administration, and to increase the clinical relevance of the study by administering the most commonly-abused formulation of hydromorphone. This will also extend the time course of hydromorphone effects, which will help us to achieve our study aims. When administered orally, hydromorphone is rapidly absorbed through the gastrointestinal tract and subjected to extensive first-pass metabolism. Exposure to hydromorphone is proportional to the dose range, with *in vivo* bioavailability of an 8mg tablet being approximately 24%. Following oral administration, peak plasma level of hydromorphone is generally attained in 30 – 60 minutes, and approximately 95% of hydromorphone is metabolized to hydromorphone-3-glucuronide via glucuronidation in the liver. There is no apparent effect of sex on the pharmacokinetics of hydromorphone.

- c. Justification and safety information if non-FDA approved drugs without an IND will be administered.

N/A

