## 7. Study Statistics

a. Primary outcome variables. The primary outcome variables are self-reported ratings of drug high and liking, changes in pupil diameter and blood pressure, pain threshold on 2 laboratory measures of pain, and analgesic efficacy in response to laboratory-induced pain. We expect that individuals with the minor allele of the A118G SNP and other

tagging SNPs across the OPRM1 gene will find hydromorphone more reinforcing (e.g., higher self-report ratings of high and drug-liking) and exhibit greater opioid-induced physiological changes (e.g., pupil diameter, blood pressure). Research also suggests the OPRM1 gene may also confer greater sensitivity to the negative effects of opioids, which may be observed as measuring greater ratings of nausea. We also hypothesize the minor allele and other tagging SNPs across the OPRM1 gene will produce higher pain threshold on 2 laboratory measures of pain, and lower analgesic efficacy in response to laboratory induced pain.

**b. Secondary outcome variables.** Decreases in cortisol levels as a function of the degree of pleasant effects of hydromorphone and painful stimuli, delay-discounting curves, and the effect of sex on all outcome measures. We hypothesize that individuals with the minor alleles will have greater decreases in cortisol levels as a function of the degree of pleasant effects of hydromorphone, lower cortisol in response to painful stimuli, and steeper discounting curves on a delay-discounting task. Finally, although we expect that the A118G will be associated with these effects, we hypothesize that several of the additional OPRM1 tagging SNPs will contribute to effect magnitude.

**c. Statistical plan including sample size justification and interim data analysis:** The aims of the proposed study will explore the impact of genetic variation across the OPRM1 gene on hydromorphone response. There are specific steps we describe below to assure that we interrogate all known functional variation across the OPRM1 gene, adequately cover all other variation using appropriately selected tagging SNPs, prevent spurious associations due to population stratification by accounting for local ancestry, and properly control the Type I error rate.

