**Association Model:** Our primary goal is to demonstrate the impact of SNP variation across OPRM1 on variability in response to hydromorphone across time and dose. Association analyses will be performed by modeling genotype at each SNP in a general linear model. In its simplest form this test, commonly termed the measured genotype analysis (137), models the influence of genotypic variation at a given locus on variation in the quantitative trait, essentially a one-way Analysis of Variance (ANOVA). This approach provides a distinct advantage in that it can easily be extended to a two-way ANOVA to model genotype effects across 3 different doses of drug. In addition, the flexibility of the GLM allows incorporation of ancestry covariates and environmental moderators or mediators. We will examine the impact of OPRM1 at each time-point in separate analyses and account for the multiple testing using LD-adjusted Bonferroni correction (see below).

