**Analysis of pain testing sessions:** We hypothesize that OPRM1 SNP variants will exhibit greater pressure pain thresholds, greater CPM efficiency, lower hydromorphone-related analgesia, and lower cortisol stress response than participants with the major allele, and that results will be positively correlated with response to self-report and physiologically-mediated hydromorphone drug effects collected during days 3-5. Pressure pain threshold will be estimated by averaging the results of the 2 administrations to radiobrachialis and quadriceps muscle groups. We will generate a CPM index for each participant [(mean pressure pain threshold during cold pressor)/(mean pressure pain threshold prior to cold pressor)] x 100 (90). These values will provide a quantitative measure of percent change in the test stimulus (i.e., pressure point threshold). Mixed effects regression models with a random intercept will be used to compare dependent variables (pressure pain threshold, DNIC threshold, DNIC index) as a function of within-subject drug effects (placebo vs. hydromorphone), and between-subject effects of OPRM1 SNP analysis will be conducted as specified in Aim 1. Gender, age, and race have been associated with response to pain and the CPM test (146-148). Gender will be evaluated using independent subgroup analyses and age and race will be included as covariates. Finally, subscale scores of self-report measures of pain and coping strategies will be compared between the two genotype groups using independent samples t-tests, and drug identification data will be compared using a chi-square for each drug condition. We expect that both experimental manipulations will induce pain in the minor and major allele groups, and that participants with the minor allele will demonstrate lower sensitivity to pain (e.g., greater pressure pain magnitudes), lower NRS ratings of pain, lower cortisol response to painful stimuli, and lower analgesic relief from hydromorphone compared to the major allele participants.

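### Doses are fixed in milligrams and no planned model includes body weight, so a male-female difference in hydromorphone response cannot be separated from dose per kilogram

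*Combined protocol and SAP*

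**What the plan says.** Section 4a sets the dosing: "Participants will receive double-blind doses of oral hydromorphone (2mg, 4mg, 8mg) (99-102) or weight and color-matched placebo". The weight mentioned there is that of the capsule; nothing in the protocol scales the dose to the participant. The only body-size item is an exclusion in Table 1 of section 5, "BMI >30 (obese category", which cannot be applied without measuring height and weight.

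On sex, section 7b lists "the effect of sex on all outcome measures" among the secondary outcomes, while section 2 calls the contribution of sex an exploratory aim. Section 9 asks, of the genotype effect, "whether this effect differs as a function of gender".

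On covariates, the Association Model paragraph of section 7c says that "the flexibility of the GLM allows incorporation of ancestry covariates" and leaves room for further moderators that it does not name. For the pain sessions, section 7c says: "Gender will be evaluated using independent subgroup analyses and age and race will be included as covariates". Section 5 adds birth control as a possible covariate. Weight, BMI and dose per kilogram are named in no model.

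On exposure, section 6b states: "There is no apparent effect of sex on the pharmacokinetics of hydromorphone". Section 6a says much the same of metabolism. Neither mentions body weight.

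**The concern.** With fixed doses, milligrams per kilogram fall as weight rises, and are higher on average in whichever sex is lighter. If response depends on dose per kilogram, a male-female difference in high, liking, pupil change, nausea or analgesia mixes two explanations, and the planned outputs cannot separate them. The protocol takes care elsewhere with this comparison: it restricts enrolment by menstrual phase to limit hormonal influence. Section 7d also sends subjective response by unlabelled sex group to the mid-point panel, which may end the study if a result is judged to be established. So the sex contrast has some weight despite its exploratory label.

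For genotype the issue is precision. Differences in response that track weight remain in the residual of a study with 100 completers, or 50 in each sex.

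**Working it through.** The plan gives no figure on body size to reproduce. From the documents: fixed doses of 2, 4 and 8 mg; 100 completers, 50 per sex; BMI no higher than 30; alpha .001 for the genotype tests (section 7c). **Everything else below is an assumption**: heights, a lower BMI of 18.5, mean BMI 25 in both sexes, the spread of weight, and a response slope of 0.5-1.0 between-person SD per doubling of mg/kg.

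1. **Extreme range of dose per kilogram.** Weight = BMI × height². 18.5 × 1.55² = 44.4 kg and 30 × 1.90² = 108.3 kg. The 8 mg dose is then 0.18 to 0.07 mg/kg, a 2.4-fold range against the 2-fold step between adjacent active doses. This pairs the shortest, leanest person with the tallest, heaviest, so it is an outer bound and not a typical spread.

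2. **Average difference between sexes.** With mean heights of 1.63 and 1.77 m: 25 × 1.63² = 66.4 kg and 25 × 1.77² = 78.3 kg. Ratio 78.3/66.4 = 1.18; log2(1.18) = 0.24 of a doubling.

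3. **Shift in the sex contrast.** 0.24 × 0.5 to 0.24 × 1.0 = 0.12 to 0.24 SD. Standard error for 50 v 50 = √(1/50 + 1/50) = 0.20 SD.

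4. **Chance of declaring a sex difference when sex itself does nothing.** By the normal formula, a shift of 0.12-0.24 SD gives about 9-22% at two-sided .05 and about 0.4-1.8% at .001. The plan sets no alpha for a sex main effect, so neither rate belongs to the plan.

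5. **Precision of the genotype test.** Variance removed = (slope × SD of ln weight / ln 2)². With SD of ln weight 0.15-0.20:
   - smallest: (0.5 × 0.15 / 0.693)² = 1.2%, equivalent N = 100/(1 − 0.012) = 101;
   - largest: (1.0 × 0.20 / 0.693)² = 8.3%, equivalent N = 100/(1 − 0.083) = 109.

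   A test with exactly 80% power at .001 would rise to about 82.9% if weight explained 5% of the variance, and to 85.7% if it explained 10%.

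6. **Cost to the adjusted sex contrast.** The standard error grows by √(1 + D²/4), where D = ln(mg/kg ratio) / SD of ln weight. With SD 0.15, a ratio of 1.10 gives D = 0.64 and a factor of 1.05; a ratio of 1.25 gives D = 1.49 and a factor of 1.25. The increase is about 5-25%, before any offset from lower residual variance.

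If response does not depend on body size, the shift in step 3 and the gain in step 5 are both zero.

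**The case against.** - **The protocol argues against a sex route through exposure.** This is the strongest point. If exposure at a fixed dose does not differ by sex, the mg/kg path to a sex difference largely closes. It weakens the concern but does not remove it: the statements in sections 6a and 6b do not address body weight, and do not say whether exposure was compared at a fixed dose or after scaling to weight. Nor do they bear on spread within each sex, although that matters for precision and not for the sex contrast.
- **Sex is exploratory.** This stands and limits the severity.
- **Section 9 asks about something else.** A reader might infer that the genotype-by-sex question is confounded by weight. The documents do not support that. Within one sex, weight confounds genotype only if the two are associated, which nothing suggests. Weight would otherwise matter there only if the genotype effect itself changes with dose per kilogram.
- **Placebo-session pain thresholds have no dose-per-kilogram component.** This stands; the point covers drug-response outcomes only.
- **Weight may lie on the path from sex to response.** Also right. Adjustment changes the question from the total sex difference to the difference at equal weight, so the adjusted result should stand beside the unadjusted one and not replace it.
- **The slope has no source.** Section 6a reports the lowest piloted doses as inactive in the cited study, yet also describes the chosen doses as producing detectable effects. The slope is therefore unsettled.

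**Conclusion.** The point holds for hydromorphone-response outcomes. Doses are fixed, the plan compares the sexes, and no model includes a measurement that the eligibility criteria already require. An unadjusted sex difference would therefore be open to two readings. The effect could be a shift of 0.12-0.24 SD under the assumed weights and slopes, and it could be zero.

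A reader might infer that the sex analysis has a false-positive rate of 9-22%. The documents do not support that: the rate needs an assumed slope and an alpha of .05 that the plan does not set for sex, and at .001 it is about 0.4-1.8%. A reader might also infer that the genotype results are biased or seriously underpowered for want of this covariate. They are not shown to be: the gain is one of precision and is modest, about 101-109 equivalent participants instead of 100.

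This is a cheap improvement of low to moderate severity.

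**What to change.** In section 7c, pre-specify log body weight at screening, with its interaction with drug or dose, as a covariate in the Association Model for drug response and in the hydromorphone-effect part of the pain models. Use one common centring value for both sexes, so that estimates from the separate sex subgroups refer to the same weight.

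Report each sex contrast with its confidence interval twice: without the weight term (total sex difference) and with it (difference at equal weight). Interpret the change in the estimate. Do not use retained or lost significance as the criterion: the adjusted standard error is wider, so lost significance would not show that weight explains the difference.

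The cost is a few sentences and no new measurement. The terms use two degrees of freedom if drug is binary or dose is linear (weight plus one interaction), and four if dose has four categories (weight plus three). The adjusted sex contrast has a standard error about 5-25% wider under the assumptions above. Fixing this in advance matters, because adding weight after seeing a sex difference would be a data-driven choice. No change to the doses is proposed.
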